### Safety Monitoring & Unanticipated Event Reporting

Adverse events will be evaluated regarding their relevance and significance to the study.

Unanticipated adverse events will be reported to the IRB if the AE is unexpected, serious, and has implications for the conduct of the study. The relationship of the unanticipated, serious adverse event to research participation will be determined by the PI. The PI will report promptly to the IRB any adverse events that are unanticipated and involve direct harm to subjects and any unanticipated events that involve risk but not direct harm to the subject according the ORIC SOPs.

An SAE that is study related, unexpected, fatal or life-threatening will be reported to the IRB as soon as possible but no later than 5 calendar days of becoming aware of the event. An SAE that is unexpected but not fatal or life-threatening will be reported to the IRB as soon as possible but no later than 10 calendar days after first knowledge. The clinical research coordinator will be monitoring and collecting all adverse events.

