## OFFICE OF HUMAN RESEARCH PROTECTION

**Study Design** – The two standard of care corticosteroids used for trigger finger treatment are betamethasone and methylprednisolone. Both injections are effective in treating trigger finger and the decision of which to use in treatment is currently a matter of the current practice and physician preference. There is no literature comparing the side effects, specifically flare reactions between these two treatments. Our goal through this randomized trial is to see whether there is a difference between these two corticosteroids in inducing flare reactions and if there are any differences in the peak level of pain and its duration. We will carry out a double-blinded randomized trial enrolling patients into one of the two treatment groups. The volume of the doses of steroid to be given will be standardized to 1 cc of either methylprednisolone (40 mg) or betamethasone (6 mg). We will instruct patients who meet the inclusion criteria to complete a visual analog scale (VAS) of their pain (1-10) prior to the injection, immediately after the injection, five minutes after the injection, and once a day for a minimum of 7 days after the injection. The incidence, intensity, time to peak and time to resolution of the flare reactions (defined as a 2-point increase from pre-injection pain) will be assessed and compared between the two groups. Findings indicating a statistically significant difference in the incidence and/or intensity of the flare reactions would be clinically significant and would be evidence supporting the switch of current standard practice to one corticosteroid over the other. Patients will only receive a single, standard of care, trigger finger injection on the day they present to the clinic. The next 7 days, up to two weeks if needed, of follow-up will only be a single short survey question to determine pain level.

Patients will be identified by the surgeon on the day they present to clinic, and will be recruited and consented by the study personnel. Data will be collected from the patient and stored in the REDCap server. There is not more than minimal risk involved.

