**REFERENCES:** See References section**Objectives**

Two common corticosteroids used for trigger finger treatment are betamethasone and methylprednisolone. Both injections are effective in treating trigger finger and the decision of which to use in treatment is currently a matter of the current practice and physician preference. There is no literature comparing the side effects, specifically flare reactions between these two treatments. Our goal through this randomized trial is to see whether there is a difference between these two corticosteroids in inducing flare reactions and if there are any differences in the peak level of pain and their duration.

Findings indicating a statistically significant difference in the incidence and/or intensity of the flare reactions would be clinically significant and would be evidence supporting the switch of current practice to one corticosteroid over the other.

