**Study Design & Methodology**

The two standard of care corticosteroids used for trigger finger treatment are betamethasone and methylprednisolone. Both injections are effective in treating trigger finger and the decision of which to use in treatment is currently a matter of the current practice and physician preference. There is no literature comparing the side effects, specifically flare reactions between these two treatments. Our goal through this randomized trial is to see whether there is a difference between these two corticosteroids in inducing flare reactions and if there are any differences in the peak level of pain and its duration. We will carry out a double-blinded randomized trial enrolling patients into one of the two treatment groups. The volume of the doses of steroid to be given will be standardized to 1 cc of either methylprednisolone (40 mg) or betamethasone (6 mg). We will instruct patients who meet the inclusion criteria to complete a visual analog scale (VAS) of their pain (1-10) prior to the injection, immediately after the injection, five minutes after the injection, and once a day for a minimum of 7 days after the injection. The incidence, intensity, time to peak and time to resolution of the flare

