## OFFICE OF HUMAN RESEARCH PROTECTION

reactions (defined as a 2-point increase from pre-injection pain) will be assessed and compared between the two groups. Findings indicating a statistically significant difference in the incidence and/or intensity of the flare reactions would be clinically significant and would be evidence supporting the switch of current standard practice to one corticosteroid over the other. Patients will only receive a single, standard of care, trigger finger injection on the day they present to the clinic. The next 7 days, up to two weeks if needed, of follow-up will only be a single short survey question to determine pain level.

All survey data will be collected from the patient in real-time, but the study will include a retrospective chart review to collect demographic information, injection specifics, etc.

Data to be collected: information from your existing medical records, and new information about you that is created or collected during this study, such as: history and physical information pertaining to trigger finger, nursing and staff notes pertaining to trigger finger, identifiers (name, MRN), demographic data (age/date of birth, sex, dominant hand), patient reported outcome measures scores, comorbidities (tobacco use, diabetes, fibromyalgia).

This study does not involve more than minimal risk. Risks from participation in this study include typical risks associated with a trigger finger injection: pain at injection site, soreness, etc.

The subject will receive no direct benefits. Knowledge gained from this study could help change standard of care procedures for trigger finger injections to best limit flare reactions afterward.

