### **Confidentiality & Privacy**

#### ***Confidentiality –***

The data will be stored in the study REDCap, maintained by the WVCTSI. Identifiers will be stored in a separate location from the record ID and only study team members will have access to the information. Data will be destroyed 3 years after study closure. All study activity, such as medical record reviews, patient phone calls for survey responses, etc will be conducted in a private location where incidental viewing could not occur. Any physical copies of patient data collected will be stored in a locked desk drawer or file cabinet at the University Town Center clinic.

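### All adverse events are to be collected, but the only scheduled follow-up item is a pain score, so later non-pain events are likely to be under-ascertained in both groups

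*Combined protocol and SAP*

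**What the plan says.** Under Safety Monitoring & Unanticipated Event Reporting, the protocol assigns the task to one person: "The clinical research coordinator will be monitoring and collecting all adverse events". The section then sets IRB reporting limits of 5 and 10 calendar days, counted from when the team learns of a serious event. It gives no question, form, schedule or collection window.

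The Study Design text in the Research Summary, and again Study Design & Methodology, describes what happens after the injection visit: "The next 7 days, up to two weeks if needed, of follow-up will only be a single short survey question to determine pain level". No return visit is described.

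Other sources of information are mentioned:

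- On the day of injection, pain is scored "prior to the injection, immediately after the injection, five minutes after the injection".
- Study Design & Methodology says that "the study will include a retrospective chart review to collect demographic information, injection specifics, etc". Its data list includes "history and physical information pertaining to trigger finger, nursing and staff notes pertaining to trigger finger".
- Confidentiality & Privacy refers to "medical record reviews, patient phone calls for survey responses".
- The Statistical Analysis Plan section says that a data safety monitoring plan exists, without giving its content. It names only flare outcomes for comparison between groups.

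The Objectives give the motivation: "There is no literature comparing the side effects, specifically flare reactions between these two treatments". They add that a significant difference in flares would support moving practice to one of the two drugs.

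**The concern.** The protocol promises complete collection of adverse events and, separately, restricts follow-up contact to pain. A coordinator who follows the text asks every patient about pain each day for 7 to 14 days and asks nobody about anything else. What reaches the adverse-event record then depends on who volunteers information and who has a note written.

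Two things are at stake.

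- The result is meant to inform a choice between two drugs on the basis of side effects. If other harms are not asked about, a short list of non-flare events may reflect the method of collection rather than the drugs.
- The 5- and 10-day reporting limits run from awareness. With passive collection, awareness may come late or not at all.

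**Working it through.** The point rests on reading the sections against each other. The plan gives no figure for adverse events, so there is none to reproduce.

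**Step 1: can each named route detect a non-pain event after the patient leaves?**

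| Route | Where described | What it can detect |
|---|---|---|
| Daily survey, 7 to 14 days | Study Design; Study Design & Methodology | Pain level only |
| Phone calls | Confidentiality & Privacy | Made to obtain the survey response, so the scheduled content is the same pain item; a patient may volunteer more |
| Clinic contact | Study Design & Methodology | Last scheduled assessment is five minutes after injection; immediate events only |
| Chart review | Study Design & Methodology | Adverse events not named as an item; the notes listed are those about trigger finger; no return visit is planned that would generate a note |
| Safety monitoring plan | Statistical Analysis Plan | Said to exist; content not given |

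Two routes remain for a later non-pain event: the patient mentions it unprompted, or it appears in a trigger-finger note. Both are passive. A problem treated elsewhere, or unrelated to the digit, need not appear in either.

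**Step 2: what could the event data show at best?** Suppose every patient is asked and none in a group reports an event. The one-sided 95% upper bound on the true rate is

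1 − 0.05^(1/n).

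Group sizes: 30 is the stated minimum per group, and 40 is the upper end of the stated 30–40 per group. Total enrolment of 80–100 gives 80/2 = 40 to 100/2 = 50 per group, assuming equal allocation, which the protocol does not state.

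- n = 30: 1 − 0.05^(1/30) = 0.095, or 9.5%
- n = 40: 1 − 0.05^(1/40) = 0.072, or 7.2%
- n = 50: 1 − 0.05^(1/50) = 0.058, or 5.8%

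The bounds for 40 and 50 require every enrolled patient to be followed. The protocol itself expects some loss of survey data.

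**Step 3: what does passive collection do to these bounds?** Let s be the share of true events that reach the record. The recorded rate is s × p, so zero recorded events bounds the true rate p at [1 − 0.05^(1/n)] / s. This is larger than the Step 2 figure whenever s is below 1. The documents give no basis for a value of s, so the loss cannot be put as a number.

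**Step 4: does the chart review need a fixed window?** Under Study Duration & Timeline, enrolment may take up to 12 months and data collection ends 3–6 months after that. If charts were searched to the end of data collection, the first patient could be observed for 12 + 3 = 15 to 12 + 6 = 18 months, and the last for only 3–6 months. Counts would then mix very different observation times, so the window should be the same for every patient.

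**The case against.** The strongest reply is that the two statements are compatible. The pain-only sentence limits what patients are surveyed on; it does not forbid recording adverse events by other means. A coordinator who phones patients, reads trigger-finger notes and logs whatever emerges complies with both. Elicitation instructions may also sit in the safety monitoring plan or in the consent form, neither of which was available for this review. Finally, the stated aim is flare reactions, and the protocol promises neither a comparison of other harms nor a conclusion that there were none.

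Much of this stands. A reader might infer that the promise cannot be kept, that every non-pain event will go unrecorded, or that zero recorded events would carry no information. The documents do not support those readings: volunteered reports and notes can capture some events, particularly those that lead to care. A reader might also infer that the flare result is compromised. It is not. Flare is defined from the change in VAS alone and needs no adverse-event question.

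What the reply does not supply is a method. The routes it relies on are not described as adverse-event collection, and none asks patients a question other than pain. If the monitoring plan does contain such a question, the pain-only wording in the two design sections is wrong and still has to be corrected.

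**Conclusion.** The concern holds in a limited form. The protocol promises collection of all adverse events but, in the text available, describes no systematic elicitation. Non-pain events after the clinic visit are left to passive capture and are likely to be under-ascertained in both groups. By how much is unknown.

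This is a gap in safety ascertainment, not a threat to the main comparison. Closing it would not make the trial informative about uncommon harms: the 5.8%–9.5% bounds show that non-flare events can only be described. It would, however, let a reader of a recommendation to switch drugs know that other problems were asked about in the same way in both groups.

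The conclusion assumes that the unseen monitoring plan and consent form contain no elicitation procedure. If they do, what remains is a wording conflict to reconcile.

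**What to change.** - **Survey.** Amend the pain-only wording in Study Design and in Study Design & Methodology. Add one fixed yes/no item with free text on any new problem or unplanned care since the injection, asked identically in both groups on day 7 and, if follow-up is extended, on the last survey day.
- **Chart review.** Name adverse events as an item to extract, with the same fixed window after injection for every patient. On the protocol's timeline, a window of up to three months would be complete even for the last patient enrolled.
- **Reporting.** Add to the Statistical Analysis Plan a descriptive table of non-flare events by group, with the number of patients who answered the item and no hypothesis test.
- **If this is not adopted.** Reword the safety section to say that only spontaneously reported or charted events are collected.

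The cost is a slightly longer survey on one or two days already scheduled, a REDCap field and a minor amendment; no added visits or staff. The change is worth most if made before follow-up is complete, because events that were not asked about cannot be reliably recovered later.

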### Study Duration & Timeline

Enrollment: could take up to a year, depending on how long it takes to recruit enough patients.

Data Collection: 3-6 months after conclusion of patient enrollment

Analysis: 3-6 months after conclusion of data collection

Approximate end date: Two years after IRB approval.

## Section III: Informed Consent Process

### Protected Health Information (PHI)

*Identify whether your research will deal with protected health information (PHI). PHI is any information in the medical record or designated record set that can be used to identify an individual and that was created, used, or disclosed in the course of providing a health care service such as diagnosis or treatment. PHI: This is not limited to only retrospective studies and chart reviews; prospective surveys may also be contain questions regarding PHI.*

1. Names
2. All elements of dates (except year) – this includes dates directly related to an individual, including birth date, admission date, discharge date, date of death; and all ages over 89 and all elements of dates (including year) indicative of such age, except that such ages and

elements may be aggregated into a single category of age 90 or older

3. Phone number(s)
4. Electronic mail (E-mail) addresses
5. Medical Record numbers
6. Sex
7. Dominant Hand
8. Patient Reported Outcome Measures Scores
9. Comorbidities: Tobacco Use, Diabetes, Fibromyalgia
10. Related to trigger finger: history and physical information, nursing and other staff notes

### **Informed Consent Process**

Prospective subjects will be identified by the surgeon at the time of their appointment. The surgeon will inform the study coordinator of a potential participant, and the study coordinator will approach the patient for consent. Consent will occur at the WVU Medicine UTC Orthopaedic clinic, in the patient's room, at the time of the patient's appointment. Patients will be given a copy of the study informed consent form to review before signing, as well as having the study coordinator go over it with them. They will be able to ask questions at any time during the process.

### **Confidentiality & Privacy**

#### ***Confidentiality –***

The data will be stored in the study REDCap, maintained by the WVCTSI. Identifiers will be stored in a separate location from the record ID and only study team members will have access to the information. Data will be destroyed 3 years after study closure. All study activity, such as medical record reviews, patient phone calls for survey responses, etc will be conducted in a private location where incidental viewing could not occur. Any physical copies of patient data collected will be stored in a locked desk drawer or file cabinet at the University Town Center clinic.

## **Section IV: Other Considerations**

### **Conflict of Interest**

*No conflicts of interest*

**Publications, Presentations, & References**

*To be determined*

